4.2 Treatment Groups

The 2 treatment groups are rimegepant and placebo. The safety analysis sets are assessed by as-treated treatment group (i.e., actual treatment received), the full and efficacy analysis sets are assessed by as-randomized treatment group, and the enrolled analysis set is assessed overall.

If a subject receives ≥ 1 dose of the planned randomized study drug, then that subject is considered to have as-treated treatment group equal to as-randomized treatment group.

If there are non-randomized subjects who receive study drug, then the as-randomized treatment group of “not randomized” is included for the full analysis set augmented with the safety analysis set.

4.3 Subgroups

Subgroup tables present results by subgroup level and overall for subjects with nonmissing subgroup level data.

4.3.1 Efficacy Subgroups

The following efficacy subgroups are of interest for primary and key secondary efficacy endpoints and supportive endpoints for the DBT efficacy analysis set:

- Imputed randomization stratum: history of clinically relevant CV disease (yes or no; see Section 6.2.5.1)
- History of documented failure to ≥ 2 triptans with ≥ 1 reason due to lack of efficacy (yes or no; see Section 6.2.5.1).

4.3.2 Safety Subgroups

The following safety subgroups are of interest for high-level safety and supportive endpoints for the DBT and OL rimegepant safety analysis sets:

- Imputed randomization stratum: history of clinically relevant CV disease (yes or no; see Section 6.2.5.1).

Medical history of hypertension is a safety subgroup of interest for hypertension-related safety endpoints for the DBT and OL rimegepant safety analysis sets (see Section 6.2.5.3). Refer to the Core SAP for the subgroup definition.

5 SAMPLE SIZE, POWER, AND TYPE I ERROR

It is anticipated that about 90% of the 300 subjects randomized to each treatment group will have a migraine in the allotted time period of the DBT Phase, resulting in approximately 270 subjects evaluable for efficacy in each treatment group.

The sample size calculation is based on pooled results from Phase 3 single-dose migraine studies C4951054 (BHV3000-301), C4951055 (BHV3000-302), and C4951056 (BHV3000-303). Pooled response rates for migraine headache pain relief at 2 hours postdose were 57.9% for rimegepant 75 mg and 43.9% for placebo in these studies.

A total sample size of 540 evaluable subjects (270 per treatment group) will provide approximately 90% power for the primary endpoint of migraine headache pain relief at 2 hours postdose in the DBT Phase. This is based on a chi-square test with a 2-sided alpha level of 0.05, and assumes that the true response rates in the subjects unsuitable for triptan use is equivalent to the overall pooled response rates above.

Type 1 error is controlled using a 2-sided alpha level of 0.05 and hierarchical testing. First, the significance of the primary endpoint is evaluated at the 2-sided alpha level of 0.05 for rimegepant versus placebo. If the primary endpoint is not significant (i.e., $p\text{-value} > 0.05$), then any further tests on key secondary endpoints will have p-values presented only for descriptive purposes. If the primary endpoint is significant (i.e., $p\text{-value} \leq 0.05$), then the key secondary endpoints are tested hierarchically, each at a 2-sided alpha level of 0.05, in the order specified in Section 3.2.2.1. Thus, a key secondary endpoint is tested only if the preceding key secondary endpoint in the hierarchy is determined to be significant (i.e., $p\text{-value} \leq 0.05$). If a test in the hierarchy is not significant, then any further tests on endpoints in the sequence have p-values presented only for descriptive purposes, and no conclusions are drawn from those results.

For testing of other secondary or exploratory endpoints, no attempt is made to adjust for multiplicity. P-values are evaluated at an unadjusted, 2-sided alpha level of 0.05 and presented only for descriptive purposes.

6 STATISTICAL ANALYSES

All statistical analyses are performed using SAS statistical software (Version 9.4 or higher).

6.1 General

6.1.1 Programmed Output

A list of TLFs and corresponding templates are presented separately in a mock TLF document corresponding to this SAP. Refer to the Core SAP for additional details about programmed output.

6.1.1.1 Tables

Treatment Group Presentation

Treatment group presentation in tables by analysis set is shown in Table 5. Exceptions are specified in subsequent sections as needed.

Table 5 Treatment Group Presentation in Tables by Analysis Set

Analysis Set	Number of Columns	Abbreviated Treatment Group
Enrolled	1	Overall
Full, DBT efficacy, DBT safety, interim safety by treatment group and {overall}	2 to 3	Rimegepant Placebo {Overall}
OLE efficacy, OLE migraine, OL rimegepant safety by treatment group and {overall}	2 to 3	DB Rimegepant/OL Rimegepant DB Placebo/OL Rimegepant {Overall}
Follow-up safety by treatment group and overall	3	DB Rimegepant/OL Rimegepant DB Placebo/OL Rimegepant Overall

Results for study population also include overall treatment group (see Section 6.2).

Subgroup tables of efficacy endpoints have the same format as the main efficacy tables, but display each subgroup level in a separate row, and page break by subgroup level. A separate table is produced for each efficacy subgroup of interest.

Subgroup tables of non-efficacy endpoints have the same format as the main non-efficacy tables, but display each subgroup level and overall in separate columns under 1 spanning column header for each DB treatment group (rimegepant, placebo). The spanning header is not displayed for OL rimegepant safety endpoints. A separate table is produced for each subgroup of interest.

Time-to-Event Tables

Time-to-event endpoints are summarized with Kaplan-Meier tables. Refer to the Core SAP for additional details.

Time-to-event distributions of endpoints are tabulated with the following descriptive statistics: number and percentage of subjects with events; number and percentage of subjects censored in or before the last time interval; number and percentage of subjects censored in the last time interval; time-to-event median with 95% CI, first quartile, and third quartile. The 95% CI for the median is estimated using the method of Brookmeyer and Crowley.

6.1.1.2 Figures

Refer to the Core SAP for additional details.

6.1.1.3 Listings

Unless otherwise specified, by-subject listings are sorted by randomization status (randomized, not randomized), site-subject ID, and additional variables such as time points, as applicable. Listings display as-randomized treatment group abbreviated as “RMG” for rimegepant, and “PBO” for placebo for subjects in the full analysis set, and (2) “NRND” for subjects not in the full analysis set.

Listings of exposure, safety parameters, and outcomes research parameters include the following: abbreviated name of the analysis period in which the measurement was slotted (i.e., PRETRT, DBT, INT, OLRMG, FU; this does not apply to exposure); analysis visit in which the measurement was slotted (this does not apply to exposure or AEs); measurement date/time; study day derived from the measurement date, DBT day ≥ 1 derived from the measurement date, OLE day ≥ 1 derived from the measurement date, and OL rimegepant day ≥ 1 derived from the measurement date (see Section 7.3).

Refer to Core SAP for additional details about listings.

6.1.2 Statistical Methods

Refer to the Core SAP for descriptive statistics in summary tables, counting rules in frequency tables, and rounding rules.

6.1.3 Handling of Missing Data

For all binary efficacy endpoints, main analyses impute missing data as failure using methods described in Section 6.3. Sensitivity analyses of the primary endpoint impute missing data using different methods (see Section 6.3.2.2). Otherwise, all analyses are based on observed data without using imputation.

6.2 Study Population

Refer to the Core SAP for TLF contents.

6.2.1 Analysis Sets

The number of subjects in each analysis set described in Section 4.1 is tabulated by treatment group (as-randomized for the full and efficacy analysis sets; as-treated for the safety analysis sets), not randomized, and overall.

The by-subject listing of analysis sets is provided for the enrolled analysis set.

The administrative listing of randomization scheme and codes is provided for the full analysis set.

6.2.2 Enrollment

The frequency table of enrollment by country and site is provided for the enrolled analysis set. The table also displays results for the full and safety analysis sets.

6.2.3 Subject Disposition

The by-subject listing of subject discontinuation is provided for the enrolled analysis set, and is based on the DB and OLE Subject Status CRFs. This includes the following parameters:

- Reference dates: last contact date* and RTSM randomization date
- Study phase: DBT or OLE. For each study phase:
 - Last visit date, derived from visit dates from the Visit Date and Unscheduled Visit CRFs
 - DBT Phase: latest visit date in the Screening or DBT Phase analysis period
 - OLE Phase: latest visit date in the OLE Phase analysis period
 - Phase completion status: “completed”; or “not completed” concatenated with the reason for noncompletion (see Sections 6.2.3.1, 6.2.3.2, 6.2.3.3, and 6.2.3.4)
 - Next phase continuation status: “continued” concatenated with the name of the next phase (OLE or Follow-up); or “not continued” concatenated with the reason for noncontinuation (see Sections 6.2.3.2, 6.2.3.3 and 6.2.3.4).

A footnote describes the derivation of the last contact date as “* Derived as the death date (if it exists); otherwise, the maximum date collected across study population, efficacy, safety, and outcomes research parameters”.

See Section 7.1 for derived dates and Section 7.2 for analysis periods.

6.2.3.1 Subject Disposition From Enrollment to Randomization

The frequency table of subject disposition from enrollment to randomization is provided for the enrolled analysis set based on the DB Subject Status CRF, and displays the following categories:

- Randomized (identified as subjects with nonmissing RTSM randomization date)
- Not randomized (identified as subjects with missing RTSM randomization date)
 - Reasons for discontinuation (i.e., not completing the DBT Phase), including not reported. For subjects whose reason is screen failure due to inclusion/exclusion criteria, the reasons for screen failure from the Inclusion/Exclusion Criteria CRF are also displayed as subcategories.

6.2.3.2 Subject Disposition From Randomization to Treatment

The frequency table of subject disposition from randomization to treatment is provided by treatment group and overall for the randomized analysis set based on the DB Subject Status CRF, and displays the following categories:

- Treated with study drug (identified as subjects with nonmissing study drug start date)
- Not treated with study drug (identified as subjects with missing study drug start date)
 - Reasons for discontinuation (i.e., not completing the DBT Phase), including not reported.

6.2.3.3 *Subject Disposition During the DBT Phase*

The frequency table of subject disposition during the DBT Phase is provided by treatment group and overall for the DBT safety analysis set based on the DB Subject Status CRF, and displays the following categories:

- Ongoing in the DBT Phase. These are identified as subjects with missing response to the question “Did the subject complete the DBT Phase?”. This category only exists before the PCD database lock; otherwise, subjects with missing response are categorized as “Did not complete the DBT Phase”.
- Completed the DBT Phase. These are identified as subjects with “yes” response to the question “Did the subject complete the DBT Phase?”.
- Did not complete the DBT Phase. These are identified as subjects with “no” response to the question “Did the subject complete the DBT Phase?”.
 - Reasons for not completing the DBT Phase, including not reported
- Continued to the OLE Phase. These are identified as subjects with “yes” response to the question “Is the subject continuing to the OLE Phase?”.
- Did not continue to the OLE Phase. These are identified as subjects with “no” response to the question “Is the subject continuing to the OLE Phase?”. Subjects with missing response to this question after the PCD database lock are also included.
 - Reasons for not continuing to the OLE Phase, including not reported.

6.2.3.4 *Subject Disposition During the OLE Phase*

The frequency table of subject disposition during the OLE Phase is provided by treatment group/OL rimegepant and overall for the OL rimegepant safety analysis set based on the OLE Subject Status CRF, and displays the following categories:

- Ongoing in the OLE Phase. These are identified as subjects with missing response to the question “Did the subject complete the OLE Phase?”. This category only exists before the LSLV database lock; otherwise, subjects with missing response are categorized as “Did not complete the OLE Phase”.
- Completed the OLE Phase. These are identified as subjects with “yes” response to the question “Did the subject complete the OLE Phase?”.
- Did not complete the OLE Phase. These are identified as subjects with “no” response to the question “Did the subject complete the OLE Phase?”.
 - Reasons for not completing the OLE Phase, including not reported

- Continued to the Follow-Up Phase. These are identified as subjects with “yes” response to the question “Is the subject continuing to the Follow-Up Phase?”.
- Did not continue to the Follow-Up Phase. These are identified as subjects with “no” response to the question “Is the subject continuing to the Follow-Up Phase?”. Subjects with missing response to this question after the LSLV database lock are also included.
 - Reasons for not continuing to the next phase, including not reported.

6.2.4 Protocol Deviations

6.2.4.1 Relevant Protocol Deviations

The frequency table of relevant protocol deviations is provided by treatment group and overall for the full analysis set by deviation type (eligibility, subject management), category, and subcategory in the order specified in Section 9.1. Results for all relevant protocol deviation categories and subcategories are displayed, even those with 0 counts, unless otherwise specified.

The by-subject listing of relevant protocol deviations is provided for the full analysis set. This includes deviation type, category, and subcategory, which are additional sorting variables. Footnotes describe the medical dictionary and the drug dictionary as applicable.

6.2.4.2 Significant Protocol Deviations

The by-subject listing of significant protocol deviations is provided for the full analysis set, and is based on a protocol deviation external file provided by the data management vendor from a clinical trial management system. This includes deviation date, category, subcategory, and description, which are additional sorting variables. Significant protocol deviations are defined as those reported with major severity. A footnote describes the raw data source and how significant protocol deviations are identified, e.g., “Significant protocol deviations are those reported with major severity by the data management vendor in the clinical trial management system.”

6.2.5 Baseline Characteristics

Baseline characteristics include (1) demographics and other relevant baseline characteristics, (2) baseline disease characteristics (i.e., migraine history; history of CV events, conditions, procedures, and other risk factors; triptan-unsuitable criteria; and migraine characteristics at the time of DB study drug dosing), (3) medical history, and (4) nonstudy prior medications. These are detailed in Sections 6.2.5.1 through 6.2.5.4, respectively.

Baseline characteristics are tabulated for each of the following analysis sets as follows:

- DBT efficacy analysis set:
 - Baseline characteristics (1) and (2) by as-randomized treatment group and overall to support efficacy. Baseline characteristics (1) and (2) by subgroup level and overall for all efficacy subgroups of interest (except randomization stratum) described in Sections 4.3.1 for each treatment group. Results support exploratory objectives #17 and #18.

- DBT safety analysis set:
 - Baseline characteristics (1) through (4) by as-treated treatment group and overall to support safety.
 - Baseline characteristics (1) and (2) by subgroup level and overall for all high-level safety subgroups of interest described in Section 4.3.2 for each treatment group. Results support exploratory objective #17.
- OL rimegepant safety analysis set: Demographics and other relevant baseline characteristics by treatment group/OL rimegepant and overall to support OL rimegepant safety.

Baseline for a parameter (e.g., weight) is defined according to analysis set; refer to the Core SAP for details, including handling of ties on the same measurement date.

By-subject listings are provided for the enrolled analysis set for the following: demographics; migraine history; triptan unsuitable criteria; and medical history.

6.2.5.1 *Demographics and Other Relevant Baseline Characteristics*

Refer to the Core SAP for the table of demographics and other relevant baseline characteristics. Other relevant characteristics also include the following categorical variables:

- Geographic region: Australia/Europe, North America
 - North America is defined as Canada, Mexico, or United States of America.
- Previous study participation (e.g., any study, BHV3000-301, BHV3000-302, BHV3000-303, etc.)
- Randomization stratum based on actual data: history of clinically relevant CV disease (yes, no)
 - Subjects are categorized as “yes” if they have history of CV event, condition, or procedure (i.e., are in category 1, 2, or 3 in Section 6.2.5.2 “History of CV Events, Conditions, Procedures, and Other Risk Factors”).
 - Otherwise, subjects are categorized as missing if they have “no” or missing response to the question “Was a Cardiovascular History assessed?” on the History of CV Events, Conditions, Procedures, and Other Risk Factors CRF.
 - Otherwise, subjects are categorized as “no”.
- Imputed randomization stratum #: history of clinically relevant CV disease (yes, no). This is an efficacy and safety subgroup of interest (see Sections 4.3.1 and 4.3.2).
 - If the randomization stratum value based on actual data is missing, then it is imputed with the randomization stratum value from the RTSM system. Otherwise, the imputed randomization stratum value is equal to the randomization stratum value based on actual data.
 - A footnote specifies that “# Missing randomization stratum based on actual data is imputed with the randomization stratum from the RTSM system. Used in subgroup

analyses and efficacy/outcomes research analyses that use randomization stratum as a variable in models or risk stratification.”.

- History of documented failure to ≥ 2 triptans with ≥ 1 reason due to lack of efficacy. This is an efficacy subgroup of interest (see Section 4.3.1).
 - Subjects are categorized as “yes” if they meet the applicable criteria defined in Section 6.2.5.2 “Triptan-Unsuitable Criteria”, i.e., they are in the “History of documented failure to ≥ 2 triptans” category and “lack of efficacy” subcategory.
 - Otherwise, subjects are categorized as missing if they have “no” or missing response to the question “Was a Cardiovascular History assessed?” on the History of CV Events, Conditions, Procedures, and Other Risk Factors CRF.
 - Otherwise, subjects are categorized as “no”.

Note that race and ethnicity are summarized only for subjects in the United States of America, and percentages are calculated against the number of subjects in the United States of America.

The frequency cross table of randomization stratum (history of clinically relevant CV disease) from the RTSM system versus actual data is provided for the full analysis set by as-randomized treatment group and overall. Categories are:

- RTSM value of “yes” and CRF value of “yes”
- RTSM value of “yes” and CRF value of “no” or missing
- RTSM value of “no” and CRF value of “no”
- RTSM value of “no” and CRF value of “yes” or missing.

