6.2.5.2 Baseline Disease Characteristics

Migraine History

Refer to the Core SAP for the table of migraine history.

History of CV Events, Conditions, Procedures, and Other Risk Factors

Results are based on the History of CV Events, Conditions, Procedures, and Other Risk Factors CRF.

The frequency table of history of CV events, conditions, procedures, and other risk factors displays the number and percentage of subjects in the following categories and subcategories based on “yes” responses to CRF questions:

- History of CV disease (event, condition, or procedure) or risk factor. Defined as any of the 4 categories listed below.
- (1) History of CV event. Defined as any of the following:
 - Cardiac arrest

- Cerebrovascular accident
- Myocardial infarction
- Transient ischemic attack
- (2) History of CV condition. Defined as any of the following:
 - Angina pectoris (myocardial ischemia)
 - Cardiac conduction disorder
 - Coronary artery vasospasm (Prinzmetal's angina)
 - Ischemic coronary artery disease
 - Ischemic bowel disease
 - Peripheral artery disease (including claudication)
- (3) History of CV procedure. Defined as any of the following:
 - Angioplasty (with or without stent placement)
 - Carotid endarterectomy
 - Coronary artery bypass grafting
- (4) Other CV disease or risk factor. Defined as any of the following:
 - Other significant underlying CV disease
 - Uncontrolled hypertension
 - Known hypersensitivity to triptan
 - Treatment for hypertension
 - Diabetes
 - Current smoker
 - Treatment with a statin
 - Family history of coronary artery disease.

Results are displayed for all categories and subcategories, even those with 0 counts.

Triptan-Unsuitable Criteria

Results are based on the Triptan-Unsuitable Criteria CRF.

The frequency table of triptan-unsuitable criteria displays the number and percentage of subjects in the following categories:

- History of documented failure to ≥ 2 triptan medications or documented contraindication to the use of triptans. These 2 categories are defined below. The number of failure reasons are the following mutually exclusive subcategories:

- All 3 reasons: lack of efficacy, prior intolerance, and documented contraindication to the use of triptans
- Only 2 reasons
- Only 1 reason.
- History of documented failure to ≥ 2 triptan medications
 - History of documented failure to a triptan is defined as a triptan meeting all the following criteria:

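### SAP 6.2.5.1 decides who is missing for the triptan-failure efficacy subgroup from the cardiovascular-history form instead of the triptan form

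*SAP*

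**What the plan says.** SAP 6.2.5.1 introduces the variable: "History of documented failure to ≥ 2 triptans with ≥ 1 reason due to lack of efficacy. This is an efficacy subgroup of interest". It then assigns three values in order.

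1. 'Yes': "Subjects are categorized as “yes” if they meet the applicable criteria defined in Section 6.2.5.2 “Triptan-Unsuitable Criteria".
2. Missing, for those not already 'yes': "subjects are categorized as missing if they have “no” or missing response to the question “Was a Cardiovascular History assessed", with the question located "on the History of CV Events, Conditions, Procedures, and Other Risk Factors CRF". This wording occurs twice in 6.2.5.1. The first use belongs to the stratum for history of CV disease. The point here concerns the second, under the triptan variable.
3. Everyone left: "Otherwise, subjects are categorized as “no".

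For the source of the triptan information, SAP 6.2.5.2 states: "Results are based on the Triptan-Unsuitable Criteria CRF".

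SAP 4.3 gives the consequence of being missing: "Subgroup tables present results by subgroup level and overall for subjects with nonmissing subgroup level data".

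For the CV stratum only, 6.2.5.1 supplies a fallback: "If the randomization stratum value based on actual data is missing, then it is imputed with the randomization stratum value from the RTSM system". The triptan variable has none.

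**The concern.** The CV question is a sensible test of missingness for the CV stratum, because that stratum is built from the CV form. The triptan variable uses nothing from that form. Even contraindication on CV grounds is taken in 6.2.5.2 from the triptan form, so the CV form is not needed to establish a 'no'. The sentence looks carried over from the stratum definition a few lines above, and no other section corrects it.

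What is at stake is the make-up of the 'no' level. This is one of two efficacy subgroups in SAP 4.3.1. It is applied to the primary and the ten key secondary endpoints and is the sole basis for exploratory objective 18. A 'no' is often a true and informative value: under Protocol Appendix 4 a subject can enter through intolerance or contraindication alone. Such subjects should not leave the table because a different form is incomplete. Nor should a subject about whom the triptan form says nothing be counted as a known 'no'.

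**Working it through.** The plan gives no figure on this point, and the variable does not enter the sample-size calculation, so there is no number to reproduce. The check is to apply the written rule to every combination of form status and compare it with the same rule keyed to the form that holds the data.

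Inputs:
- T: does the Triptan-Unsuitable Criteria form hold data for the subject? (source form, SAP 6.2.5.2)
- F: is the failure criterion met? This is possible only if T is yes. (SAP 6.2.5.1 and 6.2.5.2)
- C: was CV history assessed? (SAP 6.2.5.1)

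Rule as written: F gives 'yes'; otherwise C 'no' or blank gives missing; otherwise 'no'.

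Form-matched rule: F gives 'yes'; otherwise no triptan-form data gives missing; otherwise 'no'.

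| Triptan form | Criterion met | CV history assessed | SAP as written | Form-matched |
|---|---|---|---|---|
| data | yes | yes | yes | yes |
| data | yes | no/blank | yes | yes |
| data | no | yes | no | no |
| data | no | no/blank | **missing** | **no** |
| none | – | yes | **no** | **missing** |
| none | – | no/blank | missing | missing |

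Two of the six combinations differ. Let *a* be the number of subjects in row 4, *b* the number in row 5, *c* the number in row 6 and *n* the number in row 3.

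- Subjects misclassified: *a* + *b*.
- Size of the 'no' level: *n* + *b* as written, *n* + *a* when form-matched; the difference is *b* − *a*.
- Size of the 'yes' level: the same under both rules, because 'yes' is assigned first.

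Adding all non-'yes' subjects with an incomplete CV form to all subjects without triptan data would give (*a* + *c*) + (*b* + *c*) = *a* + *b* + 2*c*. That overstates the error by 2*c*: subjects with both forms blank are missing either way.

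Neither *a* nor *b* is in the documents, and each may be zero. If both forms are complete for every subject, the two rules agree throughout.

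**The case against.** The strongest reply is that this hardly matters.

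- **Both gaps should be rare.** Triptan unsuitability is a documented entry criterion, and CV status is needed at randomization for stratification and the cap. A blank triptan form would also meet the SAP 9.1 deviation for no documented failure or contraindication. A missing CV value enters the cross table in 6.2.5.1 and the stratum-discrepancy deviations in 9.1, although both pool it with other values. This stands as a limit on size, but those outputs flag the gap without correcting the subgroup.
- **The variable concerns documented failure.** On this view, a subject with nothing on file arguably has none documented, so 'no' is defensible. This has some force for row 5. It does not explain row 4, and a rule that sends one blank-triptan-form subject to 'no' and another to missing according to the CV form is not coherent on either view.
- **The analysis is exploratory.** SAP 6.3.1.1 makes the subgroup comparisons unstratified, with descriptive p-values. This stands.

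Stronger readings are tempting, but the documents do not support them.

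- A reader might infer that every subject without triptan data is scored 'no'. That happens only if CV history was assessed.
- A reader might infer that the triptan-unsuitable claim is undermined. Every subject must be triptan-unsuitable to enter, so the primary analysis carries that claim.
- A reader might infer a biased treatment comparison. The loss in row 4 falls only on the 'no' level, but that concerns subgroup level, not treatment arm. Both forms record history before randomization, and the rule is the same in both arms.
- A reader might infer that an overall row in the efficacy subgroup tables shifts. SAP 4.3 mentions overall results in general, but 6.1.1.1 specifies them only for non-efficacy subgroup tables, and 6.3.1.1 refers only to subgroup levels. The effect on overall is clear only for the baseline tables by subgroup in 6.2.5.

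**Conclusion.** The rule is wrong as written and should be corrected. It tests completeness of a form that the variable does not use. Followed literally, it removes some known 'no' subjects from the subgroup tables and adds to 'no' some subjects about whom the triptan form is silent.

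The reach is narrow: exploratory objective 18 and the baseline tables by this subgroup. Within these, the 'yes' level is unchanged. The primary analysis, the testing hierarchy, the power calculation and the CV stratum do not depend on the variable. The size is *a* + *b* subjects, which cannot be estimated from the documents and may be zero.

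The conclusion assumes only that the Triptan-Unsuitable Criteria form is the source of the variable, as 6.2.5.2 says, and that the rule would be programmed as it stands. The allowance in SAP Section 7 for changing conventions in dataset specifications is made for that section and does not clearly cover a definition in 6.2.5.1.

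**What to change.** In SAP 6.2.5.1, under the triptan-failure variable only, delete the condition on the CV-history question. Replace it with: a subject who is not 'yes' is missing only if the Triptan-Unsuitable Criteria form holds no data for that subject, meaning no triptan record with a failure reason and no response to the contraindication questions; otherwise the subject is 'no'. This keeps contraindication-only subjects in 'no'. Leave the same sentence in place for the CV stratum, where it is correct.

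One limit remains: a form with the contraindication questions answered but triptan records omitted would still be scored 'no'. The form itself is not in the documents, so the wording should be checked against its actual fields.

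A footnote giving the number set to missing, by treatment group, would let readers see whether the rule affected anyone. The cost is one SAP sentence and one line of code, with no new data.
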